**SUMMARY**

Dietary interventions designed to reduce cardiovascular disease (CVD) risk by increasing consumption of particular health-promoting foods (e.g., strawberries) generally target blood pressure and LDL-C—the two endpoints recognized by the FDA for a cardiovascular health claim; however, CVD risk reduction may also be achieved via changes in emerging endpoints such as the gut microbiome. Previous research suggests that strawberries have the potential to reduce LDL-C, but it remains unclear whether there is a dose-response relationship. Moreover, few studies have evaluated effects on vascular health or characterized changes in the gut microbiome following daily strawberry consumption. Additionally, previous studies have largely been conducted among Caucasian populations. Given the demographics of the US, it is important to evaluate effects in study populations that include ethnicities that may have higher risk of type 2 diabetes and/or other CVD risk factors, such as Hispanics. We propose to examine the effects of 4 weeks of supplementation with two doses of freeze dried strawberry powder (low dose: 13 g/d and high dose: 40 g/d) on: 1) LDL-C and blood pressure; 2) gut microbiome profile; and 3) other CVD and type 2 diabetes risk factors, including glucose, insulin, and inflammatory markers. We will enroll overweight (BMI 25-36 kg/m^2) but otherwise healthy adults with moderately elevated LDL-C (>3.0 mmol/L) and/or prehypertension (120-159/80-99 mm Hg). This will optimize the potential for observing significant benefits on these outcomes. We will recruit 50 eligible participants with the expectation that at least 40 will complete the study. The placebo-controlled, crossover study design will allow for a direct comparison of dose-response within the same participant. We anticipate that the bioactive components of strawberries will reduce LDL-C and blood pressure, and modify the gut microbiome, with greater changes on the high dose. There is preliminary evidence that polyphenol-rich foods can modify gut microbiota profiles, but this would be the first study to characterize the effects of daily strawberry consumption. We are uniquely placed at the University of Arizona to enroll a larger percentage of Hispanic participants, who are often under-represented in clinical nutritional research. Results from the proposed study could strengthen the evidence for a cardiovascular health claim for strawberries and draw greater attention to strawberries as a phytonutrient-rich food that can lower LDL-C and blood pressure, and modify the gut microbiome.

## JUSTIFICATION AND LITERATURE REVIEW

Current dietary recommendations to reduce CVD risk emphasize healthy dietary patterns that include specific health-promoting foods. This type of approach, focusing on whole foods and dietary patterns, is well-suited for broad public application and targets multiple CVD risk factors—including established endpoints such as LDL-C and blood pressure, as well as more novel outcomes such as the gut microbiome. Strawberries are likely to be effective for CVD risk reduction as they are a rich source of phytonutrients such as ellagic acid, anthocyanins, quercetin, catechin, and ascorbic acid. A 40 g dose of freeze dried strawberry powder provides a substantial amount of bioactive compounds with minimal calories. Doses of freeze dried strawberry powder up to 50 g/d have also been shown to be well-tolerated for 3-12 weeks [1, 2]. Previous evidence indicates that strawberries may be effective for lowering LDL-C and blood pressure [2, 3], and the phytonutrient profile of strawberries may also produce beneficial changes in the composition of the gut microbiome [4]; however, the health-promoting potential of strawberries remains underappreciated and additional evidence is needed.

With our colleagues at the Pennsylvania State University, we previously evaluated the postprandial effects of incorporating 40 g freeze dried strawberry powder into a high fat meal [5]. The design of this investigation was based largely on a previous study by Burton-Freeman et al. [6] in which incorporation of 10 g freeze dried strawberry powder in a moderate fat meal modestly attenuated peak triglyceride responses and LDL oxidation. We found no statistically significant differences in postprandial lipemia, glycemic responses, or vascular function following the strawberry meal versus the control meal [5]. We hypothesize that these disparate findings may be due, in part, to the fact that our study population was substantially younger and had much lower total cholesterol and LDL-C levels. Therefore, we now propose to study an older population (30-65 vs. 20-50 years old) with elevated LDL-C and/or blood pressure. At the University of Arizona, we will also be able to enroll a more diverse and at-risk population given the demographics of Tucson and the proximity and accessibility of one of our clinical research facilities to underserved Hispanic communities.

Longer-term supplementation (rather than an acute dose) may also be necessary to observe significant health benefits. Previous studies indicate that regular strawberry consumption likely has the potential to improve both lipids and lipoproteins, but additional research is needed to clarify these effects. For instance, beneficial effects on lipids and lipoproteins have been found with 3-12 weeks of strawberry consumption, but doses of freeze dried strawberry powder have ranged from 10 - 50 g/d [1, 2]. Additionally, little research has directly examined potential dose-response effects. To our knowledge, the only published dose-response study is specific to postprandial glucose and insulin responses following acute supplementation [7]. With regard to longer-term supplementation, a 50 g/d dose was shown to decrease LDL-C after 12 weeks in older adults with abdominal obesity and dyslipidemia [2], whereas 6 weeks of supplementation with 10 g/d did not significantly reduce LDL-C in overweight hyperlipidemic adults [6]. This suggests that a certain dose of strawberries may be required to achieve beneficial effects but a minimum required dose has not been definitively established. Only one study that we are aware of has examined the effect of long-term effect of two different doses on LDL-C within the same study population [2]. In this population of adults with abdominal adiposity and elevated lipids, 12 weeks of supplementation with either 25 g/d or 50 g/d of freeze dried strawberry powder reduced total cholesterol and LDL-C, with greater reductions achieved on the higher dose [2]. However, interpretation of these results is limited by the parallel-arm design of this study, and no

crossover dose-response studies have been published at this time. This type of study could aid in the determination of the amount of strawberries required to optimize effects on lipids/lipoproteins as it would not be confounded by potential between-subject differences at study entry.

With respect to blood pressure, there is evidence to indicate that berry consumption (including strawberries) can lower systolic blood pressure—particularly in individuals with higher baseline blood pressure values [8]. However, we are not aware of any published results regarding the effect of longer-term strawberry consumption on other measures of vascular health in adults with elevated CVD risk. Observational evidence suggests a protective relationship as greater anthocyanin and flavone intake, such as that achieved from 1-2 servings of berries per day, has been associated with lower central blood pressure and arterial stiffness [3]. However, intervention studies are needed to demonstrate a causal relationship and clarify how this relates to other CVD risk factors.

There is increasingly strong evidence that the gut microbiome plays a key role in health and disease, and may be a modifiable target for chronic disease risk reduction. To our knowledge, the composition of the gut microbiome following strawberry supplementation has yet to be characterized using state of the art sequencing technology. Previous studies have demonstrated that other polyphenol-rich plant-based foods such as blueberries can alter the microbiota profile and increase the abundance of beneficial, commensal bacteria [4, 9]. Strawberries are rich in the polyphenols ellagitannin and ellagic acid. These compounds are not readily absorbed but can be converted by gut microbiota to urolithins, which are more bioavailable and have been shown to have beneficial properties *in vitro* [10]. Thus, changes in the gut microbiome may be one of the mechanisms by which strawberry consumption can reduce CVD risk. We propose to use high-throughput sequencing technology to characterize changes in the composition of the gut microbiome following strawberry supplementation and determine whether strawberry polyphenols can effectively upregulate bacterial species associated with beneficial health outcomes.

## **OBJECTIVES**

The proposed study will investigate whether sustained strawberry consumption can reduce LDL-C, lower blood pressure, and alter the gut microbiome. We will also evaluate whether strawberries can aid in the management of other cardiometabolic disease risk factors (e.g., fasting glucose and insulin, and inflammation). If results for these outcomes are significant, this will provide further evidence to support an FDA-approved CVD health claim for strawberries. This would encourage health professionals to recommend regular strawberry consumption as part of a healthy dietary pattern for CVD risk reduction.

### **Specific Aims**

1. To determine whether 4 weeks of freeze dried strawberry consumption improves the lipid profile (primarily LDL-C, as well as total cholesterol, HDL-C, and triglycerides) and other CVD risk factors (i.e., glucose, insulin, and inflammatory markers).
2. To determine whether 4 weeks of freeze dried strawberry consumption improves vascular function, in terms of resting brachial and central blood pressure and arterial stiffness indices (i.e., augmentation index and pulse wave velocity).
3. To identify changes in the composition of the gut microbiome following 4 weeks of freeze dried strawberry consumption.

4. To determine whether there is a dose-response effect with greater improvements achieved following high dose (40 g/d) supplementation.

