### ***Experimental Design***

We propose to conduct a 3-period randomized crossover dose-response study to evaluate the effect of freeze dried strawberries on LDL-C, vascular function, and the gut microbiome. Participants will be randomly assigned to three supplementation periods: 1) low-dose freeze dried strawberry powder (13 g/d); 2) high-dose freeze dried strawberry powder (40 g/d); and 3) a placebo powder. Each powder will be provided for 4-6 weeks, separated by a 2-week washout period/compliance break between treatment periods. Therefore, end of treatment values will be separated by at least 6 weeks (4-6 week supplementation period + 2 week break), which is sufficient for endpoints to stabilize. Total study time for participants will be approximately 16-20 weeks.

The high dose (40 g/d) will act as a proof of principle dose and is equivalent to the amount consumed acutely in our previous postprandial study. The 13 g/d low dose is equivalent to approximately 1 serving of fresh strawberries per day and represents a quantity that is easily achievable under free-living conditions. The use of both a low and high dose of freeze dried strawberry powder will allow us to investigate potential dose-response effects and determine whether benefits are achievable with smaller quantities. During each supplementation period, participants will be instructed to consume one package of study powder per day. Participants will be instructed to consume study powders in between meals and mixed with a water-based beverage to minimize the chance of other foods (e.g., dairy proteins) inhibiting absorption of strawberry bioactives. To maintain blinding and consistency in powder volume across

supplementation periods, freeze dried strawberry powder and placebo powder will be combined to achieve the low dose. For the proposed study population size (n = 50), this will require 2100 packages of each powder type (placebo, low-dose, and high-dose), provided in individually portioned packages, with the following contents:

- Placebo powder (40 g packages)
- Low-dose strawberry supplementation (40 g packages, consisting of 13 g freeze dried strawberry powder + 27 g placebo powder)
- High-dose strawberry supplementation (40 g packages, consisting of 40 g freeze dried strawberry powder)

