### ***Statistical Analysis***

Statistical analyses for blood markers of CVD risk, markers of inflammation, and vascular function measurements will be performed using SAS (version 9.4; SAS Institute). Treatment comparisons will be made between each of the supplementation periods. The mixed models procedure (PROC MIXED) will be used to test the effects of supplementation, period, and their interaction on outcome measures. Selection of model covariance structures will be based on optimizing fit statistics (evaluated as lowest Bayesian Information Criterion). Mixed models for endpoint means and change scores will be evaluated. Change scores will be calculated by subtracting baseline values from endpoint values. Means will be reported as least-squares means  $\pm$  SEM. Baseline values will be included as covariates. For all tests,  $\alpha$  will be set at 0.05.

For gut microbiome analyses, microbial DNA sequences will be quality filtered at an expected error of less than 0.5% using USEARCH v7. After quality filtering, reads will be analyzed using QIIME 1.9.0. An Operational Taxonomic Unit (OTU) table will then undergo cumulative sum scaling (CSS) normalization prior to beta diversity and alpha diversity analyses. Principal coordinates analysis (PCoA) plots and ANOSIM tests for significance will be performed using a weighted unifracs distance matrix. Linear Discriminant Analysis (LDA) effect size (LEfSe) will be used to identify potential differences in the microbial community following each intervention. Exploratory Spearman rank correlations will be performed between bacterial taxa and other physiological measurements (e.g., LDL-C, blood pressure, and inflammatory markers) to identify potential microbial signatures associated with CVD risk reduction.

The Principal investigator, Co-Principal Investigator and Authorizing Official for the University of Arizona, have reviewed and approved the proposal for consideration of funding.

  
[name] 7/17/17  
Date

  
[name] 7/17/17  
Date

 for [name], Senior VP for Research 7/26/17  
Authorizing Official for the University of Arizona Date

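### Does Aim 4 need a named deciding test before greater improvement on 40 g/d can be claimed?

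*Combined protocol and SAP*

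**What the plan says.** Specific Aims, Aim 4: "To determine whether there is a dose-response effect with greater improvements achieved following high dose (40 g/d) supplementation". The aim names no comparator, outcome or decision rule. Aim 1 ranks the lipids as "primarily LDL-C, as well as total cholesterol, HDL-C, and triglycerides", but that ranking sits inside Aim 1.

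The Summary expects that strawberry components "will reduce LDL-C and blood pressure, and modify the gut microbiome, with greater changes on the high dose". Experimental Design says that using two doses "will allow us to investigate potential dose-response effects and determine whether benefits are achievable with smaller quantities".

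Statistical Analysis says "Treatment comparisons will be made between each of the supplementation periods", and that the mixed model "will be used to test the effects of supplementation, period, and their interaction on outcome measures". It adds "Means will be reported as least-squares means" and sets alpha at 0.05 for every test. Least-squares means and pairwise comparisons imply that supplementation is a three-level factor, although this is not stated. No contrast uses the dose spacing 0, 13, 40 g/d.

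On numbers, the Summary says "We will recruit 50 eligible participants with the expectation that at least 40 will complete the study". The documents give no effect size, SD or target power.

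**The concern.** Aim 4 makes two statements: that response depends on dose, and that the high dose does better. Several planned results bear on dose, but only one bears on the second statement. The overall supplementation test and 40 g/d versus placebo can both be significant when the two strawberry doses work equally well. With no test assigned to the aim, either could be written up as a dose-response.

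A plateau is a live possibility. Experimental Design itself asks whether the smaller amount is enough, and the Justification and Literature Review says that no minimum dose is established. The Objectives section links significant results to a health claim, so a loosely supported statement about dose could carry weight.

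**Working it through.** The plan has no power calculation to reproduce. The figures below illustrate the concern under stated assumptions.

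**Inputs.** From the documents: three treatments (0, 13, 40 g/d), 40 completers, alpha 0.05. Assumed: two-sided tests, compound symmetry, no carryover, complete data, residual df = 120 − 40 − 2 − 2 = 76, and a high-minus-placebo difference of 0.44 SD of the paired difference (range 0.3 to 0.6).

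**Plateau (13 g/d and 40 g/d equally better than placebo).**

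- 40 g/d versus placebo: noncentrality 0.44 × √40 = 2.78; noncentral t power 78% (47% to 96% over the range).
- Overall supplementation test: in within-subject SD units the difference is 0.44 × √2 = 0.622, so the noncentrality is 40 × (2/3) × 0.622² = 10.3; noncentral F power on 2 and 76 df is 81% (47% to 98%).
- 40 versus 13 g/d: noncentrality 0, so it favours 40 g/d in 2.5% of trials at any effect size.
- By simulation, at least one of the first two tests is significant while 40 versus 13 g/d is not (two-sided) in 81% of trials (51% to 94%). If the last condition is that the comparison does not significantly favour 40 g/d, the figure is 84%.

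**What these figures measure.** Under a plateau both doses truly beat placebo. The 78% and 81% are therefore correct rejections. Neither test, read for what it tests, says that 40 g/d beats 13 g/d. The one planned test that does say so is wrong in favour of 40 g/d 2.5% of the time, as it should be.

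**Is that test in the plan?** Comparing every supplementation period with every other gives three pairs: high–placebo, low–placebo and high–low. The third is the natural reading of greater improvement on the high dose, and the second answers whether the smaller quantity is enough.

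**Would a linear dose contrast help?** Centred on the mean dose of 53/3 g/d and multiplied by 3, the coefficients for placebo, low and high are −53, −14, 67, with sum of squares 7494. The correlation with high–placebo is 120/√(7494 × 2) = 0.98. At 0.44 SD:

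| True shape | Low-dose share of high-dose effect | Trend | High vs placebo | High vs low |
|---|---|---|---|---|
| Linear | 13/40 = 0.325 | 80% | 78% | 46% |
| Threshold | 0 | 85% | 78% | 78% |
| Emax, half-effect at 13 g/d | 0.5/(40/53) = 0.6625 | 74% | 78% | 15% |
| Plateau | 1 | 66% | 78% | 2.5% (favouring 40 g/d) |

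The trend adds little over high versus placebo, and it also rejects in 66% of plateau trials. It does not separate a plateau from a gradient.

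**Cost of making high versus low the only route to the claim.** It reaches 80% power at a high–low difference of 2.838/√40 = 0.45 SD. Under linearity that needs a high–placebo difference of 0.449/0.675 = 0.66 SD. The 95% CI half-width is 1.992/√40 = 0.31 SD.

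**The case for a change.** The best case for a change is this. Dose-response is a separate aim and part of the trial's description, yet nothing fixes which result answers it. A plateau is plausible on the protocol's own account, and two of the planned tests would then usually be significant. Naming the deciding comparison and an outcome would take a paragraph and leave the design untouched. Low power for high versus low does not justify letting a test of another question stand in for it.

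Much of this stands. No section assigns a test to Aim 4, the figures reproduce, and the overall test and high versus placebo do not by themselves show that 40 g/d is better than 13 g/d. What does not follow is that the plan misleads. The decisive comparison will be on the page beside the others, and a reader can see whether it supports the claim. Nothing in the documents suggests that the authors would set it aside.

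The other possible additions are matters of judgement. Tying Aim 4 to LDL-C would narrow an aim that the Summary extends to blood pressure and the microbiome. A per-gram slope presumes linearity, which the literature review leaves open. A strict high-versus-low rule would report a true linear gradient of 0.44 SD as not shown in more than half of trials.

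**Conclusion.** No change is needed. The gap is a missing label on a comparison that is already planned. Aim 4's own wording identifies 40 versus 13 g/d, and the pairwise comparisons supply it. A competent analyst would rest the claim of greater improvement on that estimate and its confidence interval. A non-significant result would be read as added benefit not shown, since an interval of about ±0.31 SD cannot establish that the doses are equal.

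The 81% and 78% depend on an assumed 0.44 SD effect with 40 completers and a plateau, and they describe power against placebo. The error rate that matters for the claim is 2.5% in favour of the high dose, whatever the effect against placebo. A linear contrast would bring little gain, and fixing a single outcome would be a trade-off for the investigators to make.

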## **METHODS**

### ***Subjects & eligibility***

For this study we will recruit overweight men and women (body mass index 25-36 kg/m^2) as this is representative of U.S. adults who are at higher CVD risk and might benefit the most from increased strawberry consumption.

#### Additional eligibility criteria will include:

- 30-65 years of age
- At least one of the following:
  - LDL-C above 3.0 mmol/L (116 mg/dL)
  - Systolic blood pressure of 120-159 mmHg
  - Diastolic blood pressure of 80-99 mmHg
- Total cholesterol below 6.2 mmol/L (240 mg/dL)
- Triglycerides below 350 mg/dL

#### Exclusion criteria will include:

- Allergies to strawberries
- History of CVD, Stage II hypertension (BP  $\geq$  160/100 mmHg), kidney disease, diabetes, or inflammatory diseases such as GI disorders and rheumatoid arthritis
- Use of medications/supplements for elevated lipids, blood pressure, or glucose
- Chronic use of non-steroidal anti-inflammatory or immunosuppressant drugs
- Conditions requiring chronic use of steroids

### ***Experimental Design***

We propose to conduct a 3-period randomized crossover dose-response study to evaluate the effect of freeze dried strawberries on LDL-C, vascular function, and the gut microbiome. Participants will be randomly assigned to three supplementation periods: 1) low-dose freeze dried strawberry powder (13 g/d); 2) high-dose freeze dried strawberry powder (40 g/d); and 3) a placebo powder. Each powder will be provided for 4-6 weeks, separated by a 2-week washout period/compliance break between treatment periods. Therefore, end of treatment values will be separated by at least 6 weeks (4-6 week supplementation period + 2 week break), which is sufficient for endpoints to stabilize. Total study time for participants will be approximately 16-20 weeks.

The high dose (40 g/d) will act as a proof of principle dose and is equivalent to the amount consumed acutely in our previous postprandial study. The 13 g/d low dose is equivalent to approximately 1 serving of fresh strawberries per day and represents a quantity that is easily achievable under free-living conditions. The use of both a low and high dose of freeze dried strawberry powder will allow us to investigate potential dose-response effects and determine whether benefits are achievable with smaller quantities. During each supplementation period, participants will be instructed to consume one package of study powder per day. Participants will be instructed to consume study powders in between meals and mixed with a water-based beverage to minimize the chance of other foods (e.g., dairy proteins) inhibiting absorption of strawberry bioactives. To maintain blinding and consistency in powder volume across

supplementation periods, freeze dried strawberry powder and placebo powder will be combined to achieve the low dose. For the proposed study population size (n = 50), this will require 2100 packages of each powder type (placebo, low-dose, and high-dose), provided in individually portioned packages, with the following contents:

- Placebo powder (40 g packages)
- Low-dose strawberry supplementation (40 g packages, consisting of 13 g freeze dried strawberry powder + 27 g placebo powder)
- High-dose strawberry supplementation (40 g packages, consisting of 40 g freeze dried strawberry powder)

We will recruit participants who consume a typical American diet (i.e. not vegetarian, not engaged in a structured diet plan, and not attempting to lose weight) to limit variability in endpoint responses. Participants will be instructed to keep their diet consistent and maintain body weight and physical activity levels during the study. Participants will also maintain a daily consumption log to monitor compliance and daily intake of study powders. Participants will receive an ~14 day supply of study powders on a biweekly basis, during which time study staff will monitor body weight and review consumption logs.

